## **5.2. Analysis Populations**

### **5.2.1. Enrolled Population**

The Enrolled Population includes all subjects who were enrolled to the study.

### **5.2.2. Safety Population**

The Safety Population includes all subjects who received at least 1 dose of IP.

### **5.2.3. Efficacy Evaluable Population**

The Efficacy Evaluable Population includes all subjects who meet all eligibility criteria, and EITHER

1. Received at least 2 cycles of IP at any dose intensity and discontinued treatment for progressive disease, OR
2. Received at least 4 cycles of IP at any dose intensity and have baseline and at least two post-screening tumor assessments.

Subjects receiving the 200 mg dose will be efficacy evaluable for response if they meet the defined criteria. Subjects not eligible for the Efficacy Evaluable Population will be replaced at the discretion of the sponsor.

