**Treatment:** Subjects meeting eligibility criteria must start treatment within 21 days of signing the informed consent form (ICF). For all subsequent visits, an administrative window of  $\pm$  2 days is permitted. Treatment cycles are 21 days in duration. All evaluations should be performed prior to dosing on the visit day, unless otherwise specified. CC-486 will be administered at a dose of 300 mg orally (PO) daily (QD) on Days 1 to 14 of a 21-day cycle. However, the first 6 subjects of Asian-Pacific Island ethnicity evaluable for safety will receive CC-486 at a dose of 200 mg orally QD on Days 1 to 14 of 21 days of Cycle 1; and if well-tolerated, and there are no safety concerns, subsequent subjects of Asian-Pacific Island ethnicity will be treated at the 300 mg QD on Days 1 to 14 of a 21-day cycle.

**Response Assessment by Response Evaluation Criteria In Solid Tumors (RECIST) v 1.1:** Response assessments (tumor evaluations) should be performed at screening within 28 days before the start of investigational product (IP), and every 6 weeks ( $\pm$  5 days) from Cycle 1 Day 1 (C1D1) for the first 3 tumor evaluations and then every 9 weeks until disease progression, start of a new anticancer therapy, or withdrawal of consent from the entire study. Evaluation of response will be performed using RECIST v1.1.

An independent radiological assessment of responses will be conducted using RECIST v1.1.

Response assessments include computed tomography (CT) scan or magnetic resonance imaging (MRI) of the head and neck with supraclavicular node imaging, the chest and abdomen/pelvis,

neurological examination with facial nerve evaluation, and bone scans at baseline for all subjects. Bone scans will be repeated only if the subject is symptomatic or with known bone metastasis. The same mode of imaging for lesion evaluation at screening must be used consistently throughout the study.

All subjects with evidence of objective tumor response (CR or PR) should have the response confirmed with repeat assessments at the next scheduled scan, but after no less than 4 weeks. Response assessments must have occurred  $\geq$  6 weeks from Cycle 1 Day 1 to be considered as SD for a best response.

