## 10. EFFICACY ANALYSIS

All efficacy results will be summarized for the efficacy evaluable population. If Stage 2 is conducted, analyses will be performed for PFS and OS in addition to ORR. Column headers will be displayed as follows: 'AP 200 mg', '300 mg', and 'Total'.

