Disease control rate, a secondary efficacy endpoint, is defined as CR and PR, confirmed  $\geq 4$  weeks after the criteria for response are first met, and SD  $\geq 16$  weeks from the first treatment, based on independent radiology assessment using RECIST v1.1. The point estimate and two-sided 90% CI of DCR will be provided using the Clopper-Pearson method (Clopper, 1934).

Overall survival, another secondary efficacy endpoint, is defined as the time from first treatment to death of any cause. Subjects who did not die by the end of study or the clinical data cut-off date will be censored on the last-known-to-be-alive date or the clinical cut-off date, whichever is earlier.

The survival distribution of OS will be estimated using K-M method. The median including two-sided 90% CI will be provided. The survival rates will be provided at each 2-month interval. Kaplan-Meier curves for OS will also be presented.

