## 11. SAFETY ANALYSIS

All safety analyses will be conducted based on the safety population. Descriptive statistics will be provided by treatment dose and for total safety population.

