### 11.1. Adverse Events

Adverse events will be analyzed in terms of TEAEs which are defined as any AE that begins or worsens on or after the start of study drug through 28 days after the last dose of study drug. All AEs will be coded using MedDRA version 19 or higher.

A treatment-related TEAE is defined as a TEAE which was reported as “Suspected” on the CRF. Adverse events with a missing relationship will be treated as “treatment-related.”

The incidence of TEAE will be summarized by MedDRA SOC and PT. Severity of AEs will be graded 1 to 5 according to the CTCAE Version 4.0 or higher. For all other AEs not described in the CTCAE, severity will be assessed by the investigator as mild (Grade 1), moderate (Grade 2), severe (Grade 3), life-threatening (Grade 4) or death (Grade 5).

Tables summarizing the number and percentage of subjects experiencing TEAEs by treatment dose and for total safety population will be generated for each of the following:

- All TEAEs by SOC and PT
- All TEAEs by SOC
- All TEAEs by PT
- All TEAEs by Preferred term with Incidence of >5%
- All TEAEs by onset cycle
- Treatment-related TEAEs
- TEAEs of Grade 3 or 4
- Treatment-related TEAEs Grade 3 or 4
- All TEAEs by maximum CTCAE grade
- Treatment-related TEAEs by maximum CTCAE grade
- Serious TEAEs
- All serious TEAEs by Preferred term with Incidence of >5% Treatment-related serious TEAEs
- All treatment-related serious TEAEs by Preferred term with Incidence of >5%
- TEAEs with action of study drug withdrawn
- Treatment-related TEAEs with action of study drug withdrawn
- TEAEs with action of study drug dose reduced

- Treatment-related TEAEs with action of study drug dose reduced
- TEAEs with action of study drug dose interrupted
- Treatment-related TEAEs with action of study drug dose interrupted
- TEAEs with outcome of death
- Treatment-related TEAEs with outcome of death
- All deaths within 28 days of last dose with cause of death
- TEAEs for the following baseline subgroups (provided the number of subjects is sufficient):
  - Age (< 65 years, 65 years to < 75 years, ≥ 75 years)
  - Sex

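### OS is estimated only in subjects selected on their course after dosing, which biases it upward, and no all-treated ORR, DCR, PFS or OS is planned beside the evaluable-set results

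*SAP*

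**What the plan says.** Section 10 assigns one analysis set: "All efficacy results will be summarized for the efficacy evaluable population". Section 5.2.3 gives two routes into it for eligible subjects. The first is "Received at least 2 cycles of IP at any dose intensity and discontinued treatment for progressive disease". The second is "Received at least 4 cycles of IP at any dose intensity and have baseline and at least two post-screening tumor assessments".

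Sections 4.1 and 4.3 add that subjects who progress in Cycle 1 are not evaluable and are replaced. Section 4.1 says the same of subjects who leave the study before the first tumour assessment for a reason other than progression.

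The survival clock starts at first dose: "Overall survival, another secondary efficacy endpoint, is defined as the time from first treatment to death of any cause". PFS also runs from the start of treatment and counts death from any cause (Section 10.2).

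An all-treated set exists: "The Safety Population includes all subjects who received at least 1 dose of IP". Its use is for exposure, safety and related summaries ("All safety analyses will be conducted based on the safety population"). No ORR, DCR, PFS or OS is planned in it.

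On whether PFS and OS are analysed at all, Section 10 makes them conditional on Stage 2 being conducted. Section 10.2 states that Stage 2 was not entered, yet still plans Kaplan-Meier medians, rates and curves for both.

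**The concern.** Membership of the analysis set depends on events after the clock has started. A subject admitted by the second route must have survived to a second scan, yet that guaranteed time is counted as OS. A subject who dies earlier without stopping for progression contributes neither time nor event. A Cycle 1 progressor is also removed.

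A reader will take the OS median and survival rates as survival of treated subjects from first dose. They will describe a group from which some early deaths have been taken out. The confidence interval does not show this, because it is centred on the selected estimate. OS needs no scan to be evaluable, so the reason for an evaluable set in a response count does not carry over to it.

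**Working it through.** **1. The plan's own figure.** The Simon design in Section 4.3 (stop at 4 or fewer of 17; positive at more than 14 of 51) reproduces. Summing P(X1 = x) × P(X2 ≥ 15 − x) over x = 5 to 17, with X1 ~ Bin(17, p) and X2 ~ Bin(34, p), gives 0.0487 at p = 0.20 (stated 5%) and 0.854 at p = 0.40 (stated 85%). The count rule for evaluable subjects is sound.

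**2. Earliest entry by the second route.** Section 4.1 sets 21-day cycles and scans every 6 weeks (± 5 days) "for the first 3 tumor evaluations and then every 9 weeks until disease progression". The second scan is due 12 × 7 = 84 days after first dose, so no earlier than 84 − 5 = 79 days. Cycle 4 starts at 3 × 21 = 63 days, so the scan is the later requirement if cycles need only be started. A death before about day 79 without a stop for progression meets neither route.

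**3. OS, hand check.** Suppose OS is exponential with median m and the earliest deaths, a share q of treated subjects, are removed. The remaining curve is S(t)/(1 − q), so the apparent median is m × [1 − log2(1 − q)]. With m = 12 months (assumed):

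- q = 5%: 12 × 1.074 = 12.9 months
- q = 10%: 12 × 1.152 = 13.8 months

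**4. OS, simulation of the Section 5.2.3 rule.** The SAP gives no death, stop or post-progression rates, so these inputs are assumptions:

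- exponential time to event, median 5 months
- 0, 10 or 30% of events assigned as death without progression; a death before the detecting scan also counts as such
- 0 or 30% of progressions found off schedule
- stops for other reasons at 0, 5 or 10% per month
- median post-progression survival 6 or 12 months
- scans on the Section 4.1 schedule

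Results are evaluable minus all-treated, with cycles counted as started or fully dosed:

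| Assigned deaths without progression | Median OS (months) | 6-month OS (points) |
|---|---|---|
| 0% | +0.1 to +0.6 | +0.9 to +2.9 |
| 10% | +0.6 to +1.0 | +3.7 to +5.1 |
| 30% | +1.3 to +2.2 | +8.6 to +9.5 |

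The all-treated medians were 12.4 to 18.1 months at 10% and 10.5 to 14.3 at 30%. The share of treated subjects dying without documented progression before day 79 was 3.7 to 5.1% and 9.5 to 10.7%, so the hand check agrees. If cycles must be completed, the shifts are +0.6 to +0.9, +1.0 to +1.4 and +1.6 to +2.3 months. The shift was positive in all 108 scenarios.

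**5. Sampling error.** For 17 uncensored subjects, the 5th and 13th ordered times bound the median with 95.1% coverage (the 6th and 12th give 85.7%). With a 12-month exponential median (mean 12/ln 2 = 17.3), their expected values are 5.8 and 23.5 months.

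**6. ORR, Clopper-Pearson 90% limits.** Illustrative counts:

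- 4/17 = 23.5% (8.5 to 46.1)
- four excluded non-responders added back: 4/21 = 19.0% (6.8 to 38.4)
- one of those four a responder: 5/21 = 23.8% (9.9 to 43.7), and the difference disappears

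**7. PFS and DCR, same simulation (started or fully dosed).** Median PFS shifts by −0.01 to +0.16 months at 0 to 10% deaths and +0.15 to +0.54 at 30%. The 16-week event-free proportion, a stand-in for DCR, shifts by −0.4 to +6.1 and +6.5 to +10.2 points. The sign is not fixed, because event-free subjects who stop early for other reasons are dropped too.

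**The case against.** The evaluable set is a declared design choice. Section 4.3 sizes the study on it, Sections 4.1 and 4.3 announce the exclusions and replacements, and Section 16 lists only the Enrolled Population definition as a change from the protocol's statistical section. That stands for the Simon count. It does not justify restricting OS.

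Read literally, the Stage 2 condition in Section 10 means that OS would not be reported, so nothing would be biased. But Section 10.2 plans Kaplan-Meier PFS after saying that Stage 2 was not entered, and plans OS without any condition. The conflict is real and belongs in the fix.

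A reader might infer that the early deaths are hidden. They are not. Section 6 counts deaths, and Section 11.1 tabulates fatal TEAEs and "All deaths within 28 days of last dose with cause of death" and lists all deaths with cause. Nor do the Section 11.1 tables capture every excluded death: a subject who stops in Cycle 1 and dies around day 70 may appear only in the count and the listing. None of these yields an all-treated survival estimate.

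A reader might also infer a larger OS effect. Letting death strike independently of progression gives about +2.3 to +2.5 months, but that assumption is probably severe, and nothing in the SAP supports it over the milder cases.

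The OS direction could be offset if subjects excluded after stopping for other reasons lived unusually long. The SAP gives no reason to expect this.

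**Conclusion.** The point holds and should be fixed. Confidence is high on the structure and conditional on the size. OS as planned is biased upward: about +0.1 to +0.6, +0.6 to +1.0 or +1.3 to +2.2 months in the median at 0, 10 or 30% assigned deaths without progression, under the assumptions above. The upper end rests on the 30% figure, which the SAP does not supply. All of these are small beside an interval of roughly 6 to 23 months at n = 17.

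Two stronger readings are not supported. One is that ORR, DCR and PFS are all inflated: their direction is not assured, and the defect is the absence of an all-treated figure for comparison. The other is that the Stage 1 decision or the error rate is compromised: the Simon count was specified for evaluable subjects, its arithmetic is right, and no PFS test will be made.

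**What to change.** 1. Reconcile Section 10 with Section 10.2 by stating that PFS and OS are estimated descriptively although Stage 2 was not entered.

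2. Add to Section 10 wording such as: *ORR, DCR, PFS and OS will also be summarised for the Safety Population as supplementary analyses, added after the Stage 1 outcome was known. Subjects without an adequate post-baseline assessment count as non-responders for ORR and as not controlled for DCR. PFS and OS follow the Section 10.2 event and censoring rules; subjects with no post-baseline scan and no PFS event are censored for PFS at Day 1.* Present these beside the evaluable results, and keep the Efficacy Evaluable Population for the Simon count.

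3. Minor: reconcile the evaluability and replacement wording of Sections 4.1, 4.3 and 5.2.3. Section 4.1 replaces its named types outright, whereas Section 5.2.3 leaves replacement to the sponsor's discretion. State also whether a received cycle is one started, fully dosed or completed.

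The cost is one extra set of tables and a few lines of text. Section 4.1 already provides survival follow-up for all subjects, so no new data are needed. The tables must be labelled supplementary because they come after the Stage 1 outcome, and the all-treated OS may look less favourable.

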### **5.2.4. Pharmacokinetic Population**

The PK Population includes a subset of enrolled subjects of Asian-Pacific Island ethnicity at experienced selected sites who have evaluable pharmacokinetic data from at least 1 dose of IP.

## **6. SUBJECT DISPOSITION**

Analysis population allocation will be summarized. The number and percentage of subjects who are treated and discontinued the treatment and the number and percentage of subjects who discontinued the study will be presented for the enrolled population. Each reason for treatment discontinuation and each reason for study discontinuation collected on the CRF will be summarized in the subject disposition table.

The number and percentage of subjects who died, and the number of subjects who are in survival follow-up or lost to survival follow-up at the time of analysis will also be presented in the subject disposition table.

The number and percentage of subjects eligible or not eligible for the study, enrolled under each protocol amendment, and treated by site will be summarized.

Listings will be provided for screen failures with reason for screen failure, discontinued subjects with reason for treatment discontinuation or reason for study discontinuation included.

## 7. PROTOCOL DEVIATIONS/VIOLATIONS

Protocol deviations and violations will be identified and assessed periodically by the clinical research physician or designee following institution standard operational procedures. Prior to database lock, a final review and categorization of protocol violations or deviations will be performed by the study team. The protocol violations will be summarized using frequency tabulations for the enrolled population.

A listing of subjects with protocol deviations or violations will also be provided.

CELGENE PROPRIETARY INFORMATION

## 8. DEMOGRAPHICS AND BASELINE CHARACTERISTICS

Demographics and baseline characteristics will be summarized for the Enrolled Population, unless otherwise specified. Individual subject listings will be provided to support the summary tables.

### 8.1. Demographics and Baseline Characteristics

Age (years), height (cm), weight (kg), body surface area (BSA) (m^2), and vital signs at baseline will be summarized by sample size, mean, median, STDEV, minimum, and maximum values. Age category (< 65 years, ≥ 65 years and < 75 years, and ≥ 75 years), sex, race, ethnicity, ECOG performance status at baseline, and electrocardiogram (ECG) overall interpretation at baseline will be summarized by number and percentage of subjects in each category. Descriptive summary statistics for EBV-DNA (by real time-polymerase chain reaction [RT-PCR])) at baseline will be provided.

Age will be calculated as follows: Age = Maximum Integer ≤ ([Date of Informed Consent – Date of Birth +1] / 365.25).

BSA will be calculated as follows: BSA m^2 = 0.007184 × (weight in kg)0.425 × (height in cm)0.725 (Du Bois, 1917).

#### 8.1.1. Cancer History

The number and percentage of subjects in each of the following categories will be presented:

- Cancer diagnosis
- Current cancer type (locally advanced, metastatic)
- Stage at initial diagnosis (0, I, II, III, IVA, IVB, IVC)
- TNM Classification at initial diagnosis: T category (TX, T0, Tis, T1, T2, T3, T4), N category (NX, N0, N1, N2, N3, N3a, N3b), M category (M0, M1)
- Best response to prior therapy (CR, PR, SD, progressive disease, unknown, not applicable)

Time from initial diagnosis to first dose and time from most recent recurrence/ progression to first dose will be summarized descriptively.

### 8.2. Medical History

A summary of relevant medical history will be presented by Medical Dictionary for Regulatory Activities (MedDRA) system organ class (SOC) and preferred term (PT) for the safety population.

### 8.3. Prior Therapies/Surgeries

Any prior therapy will be collected at screening. Prior systemic anticancer therapies or other anticancer therapies will be coded to therapeutic drug classes and generic drug names using the

World Health Organization (WHO) drug dictionary. Prior cancer surgeries will be coded by MedDRA.

The number and percentage of subjects who had any prior radiation therapies, prior cancer surgeries, and prior systemic or other anticancer therapies will be presented for the safety population. Descriptive statistics (eg, the time from end of prior therapy/surgery to first dose date in months) may also be provided, if needed. The therapies/surgeries with the same sequence/regimen number will be counted as one prior therapy/surgery. For subjects who had prior systemic anticancer therapies or other anticancer therapies, the incidence by coded therapeutic drug class and generic drug name will be provided in the summary table. The summary table of incidence of prior cancer surgeries will also be provided.

#### **8.4. Prior and Concomitant Medications**

Medications reported on the Prior and Concomitant Medications CRF page will be coded to therapeutic drug classes and generic drug names using the WHO drug dictionary and will be summarized for the safety population. The Anatomical Therapeutic Chemical coding scheme of the WHO drug dictionary will be used to group medications into relevant categories for these tabulations. Individual listing of prior and concomitant medications will be provided to support the tables.

##### **8.4.1. Prior Medications**

A prior medication will be any medication started prior to the date of the first dose of study drug. A summary will be presented showing the number and percentage of subjects who took prior medications by therapeutic drug class and generic drug name, as well as the number and percentage of subjects that took any prior medication.

##### **8.4.2. Concomitant Medications**

Concomitant medication is defined as a medication that was either initiated before the first dose of study drug and continued during the study treatment, or initiated on/after the date of the first dose of study drug and within 28 days of the last dose of study drug.

A summary will be presented showing the number and percentage of subjects who took concomitant medications by WHO therapeutic drug class and generic drug name, as well as the number and percentage of subjects who took any concomitant medications.

#### **8.5. Concomitant Procedures/Surgeries**

A concomitant procedure/surgery is defined in a manner similar to the concomitant medication above. A summary will be presented showing the number and percentage of subjects who had concomitant procedures/surgeries by SOC and PT.

## **9. STUDY TREATMENTS AND EXTENT OF EXPOSURE**

Study treatment and extent of exposure summaries will be provided based on the safety population. Treatment duration, dose exposure, number of cycles, number of doses, cumulative dose, dose intensity, average daily dose, relative dose intensity, dose reduction, and dose interruption, number of subjects dosed at each cycle and maximum number of cycles received per subject will be summarized. Individual subject listings of exposure to study drug will be provided. Column headers will be displayed as follows: 'AP 200 mg', '300 mg', and 'Total'.

### **9.1. Treatment Duration**

The treatment start date is the date of the first dose of study drug and the treatment end date is the date of the last non-missing dose of study drug.

Treatment duration (in days) is calculated as (the treatment end date – the treatment start date + 1). Summary statistics for treatment duration (in days) will be provided. Descriptive statistics will be provided for the total number of treatment cycles subjects received and for the number of doses received.

### **9.2. Dose Exposure**

Dose exposure (days) for overall is defined as the total number of actual days on CC-486 (dose > 0 mg) during treatment phase.

### **9.3. Cumulative Dose**

Cumulative dose is defined as the sum of all administered doses in mg during the treatment period across all cycles.

### **9.4. Dose Intensity**

Dose intensity reported in mg/day will be calculated as the cumulative dose divided by the treatment duration in days which is defined in Section 9.1 above.

